9.4.2 Clinical Laboratory Assessments

All statistical analyses of laboratory values will be performed using SI units. Continuous hematology, clinical chemistry and coagulation (Part D only) results including baseline and change from baseline values will be summarized at each scheduled time point by treatment group/treatment sequence for each part using descriptive statistics.

For Part D, the number and percentage of subjects meeting at least 1 threshold analysis criterion event, during the TE period for Treatment Period, will be summarized by treatment group. The threshold analysis criteria are provided in [Appendix D](#).

Clinically significant abnormal laboratory findings will be reported as AEs.

9.4.3 [Electrocardiogram](#)

A summary of raw values and change from baseline values will be provided for each scheduled time point by treatment group/treatment sequence for each part during the TE Period for the following 12-lead ECG measurements using descriptive statistics: RR interval, PR interval, QT interval, QTcF interval, QRS duration, and Heart Rate (beats per minute).

For Part D, the number and percentage of subjects meeting at least 1 threshold analysis criterion during the TE period for the Treatment Period will be summarized by treatment group. The threshold analysis criteria are provided in [Appendix D](#).

In addition, the number and percentage of subjects by maximum value of QT/QTc intervals during the TE period, categorized as ≤ 450 msec, >450 msec and ≤ 480 msec, >480 msec and ≤ 500 msec, and >500 msec, as well as maximum change from baseline value of QT/QTc intervals during the TE period, categorized as ≤ 0 msec, >0 msec and ≤ 30 msec, >30 msec and ≤ 60 msec, and >60 msec will be tabulated based on scheduled and unscheduled 12-lead ECG measurements by treatment group/treatment sequence for each part.

Clinically significant abnormal findings will be reported as AEs.

9.4.4 [Vital Signs](#)

A summary of raw values and change from baseline values will be provided for each scheduled time point by treatment group/treatment sequence for each part using descriptive statistics for the following vital signs measurements: BMI (kg/m^2), weight (kg), height (cm), systolic and diastolic blood pressure (mm Hg), body temperature ($^{\circ}\text{C}$), pulse rate (beats per minute), and respiratory rate (breaths per minute).

For Part D, the number and percentage of subjects meeting at least 1 threshold analysis criterion during the TE period for the Treatment Period will be summarized by treatment group. The threshold analysis criteria are provided in [Appendix D](#).

In addition, a listing containing individual subject vital signs values will be provided. This listing will include data from both scheduled and unscheduled visits.

[figure not shown]
Clinically significant abnormal findings in vital signs will be reported as AEs.

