a On dosing days, assessments will be performed before dosing, unless noted otherwise.b Additional PK samples and safety assessments may also be performed at the discretion of the investigator. See [Section 9.1.1.4](#) for details.c Subjects will be discharged from the CRU on Day 16 after completion of the study visit assessments.d Weight will be measured with shoes off.e Standard 12-lead ECGs will be performed in the supine position after the subject has been at rest for at least 5 minutes. The ECG will be done before any other procedures that may affect heart rate, such as blood draws. On Days 1 and 9, ECGs will be collected before dosing and approximately 1, 3, 5, and 6 hours ( $\pm$  15 min) after dosing.f Vital signs will be performed after the subject has been at rest for at least 5 minutes.g Blood samples for PK assessments will be collected on Days 1 and 9 before dosing (0 hours), and at 1, 1.5, 2, 3, 4, 5, 6, 8, 12, 24 (Days 2, 10), 36 (Days 2, 10), 48 (Days 3, 11), 72 (Days 4, 12), 96 (Days 5, 13), 120 (Days 6, 14), 144 (Days 7, 15), and 168 (Days 8, 16) hours after dosing. Acceptable PK sampling windows are provided in [Table 11-1](#). At the Safety Follow-up Visit, a single blood sample for PK analysis will be collected.h Subjects will be randomized 3:1 to receive VX-121 or placebo. Study drug will be administered in the fed state ([Section 9.6.1](#)).i All subjects will receive open-label VX-121. Study drug will be administered in the fed state and with milk ([Section 9.6.1](#)).j All medications taken from 28 days before the first dose of study drug through the end of the study will be recorded.

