**Table 3-4 Study VX17-121-001: Part A, Cohort A9, Treatment Period and Safety Follow-up Visit**

Event/Assessment a	Study Day										Safety Follow-up (7 to 10 Days After Last Dose of Study Drug) b
	-1	1	2	3,4,5, 6,7,8	9	10	11,12,13, 14,15,16	17	18	19,20,21, 22,23,24	
Inpatient days	X	X	X	X	X	X	X	X	X	X c	
Outpatient visit											X
Weight d	X										
Standard 12-lead ECG e	X	X			X			X			X
Vital signs f	X	X	X	X	X	X	X	X	X		X
Full physical examination	X										X
Serum chemistry	X		X			X			X		X
Hematology	X		X			X			X		X
Blood for PK analysis g		X	X	X	X	X	X	X	X		X
Drug test (urine or blood), including cotinine	X										
Alcohol test (urine, blood, or breath)	X										
Urinalysis											X
Study drug administration h			X		X			X			
Adverse events	Continuous from signing of ICF through Safety Follow-up Visit										
Medications review i	Continuous from signing of ICF through Safety Follow-up Visit										
Treatment and procedures review	Continuous from signing of ICF through Safety Follow-up Visit										

a On dosing days, assessments will be performed before dosing, unless noted otherwise.

b Additional PK samples and safety assessments may also be performed at the discretion of the investigator. See [Section 9.1.1.4](#) for details.

c Subjects will be discharged from the CRU on Day 24 after completion of the study visit assessments.

d Weight will be measured with shoes off.

e Standard 12-lead ECGs will be performed in the supine position after the subject has been at rest for at least 5 minutes. The ECG will be done before any other procedures that may affect heart rate, such as blood draws. On Days 1, 9, and 17, ECGs will be collected before dosing and approximately 1, 3, 5, and 6 hours ( $\pm$  15 min) after dosing.

f Vital signs will be performed after the subject has been at rest for at least 5 minutes.

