g Blood samples for PK assessments will be collected on Days 1, 9, and 17 before dosing (0 hours), and at 1, 1.5, 2, 3, 4, 5, 6, 8, 12, 24 (Days 2, 10, 18), 36 (Days 2, 10, 18), 48 (Days 3, 11, 19), 72 (Days 4, 12, 20), 96 (Days 5, 13, 21), 120 (Days 6, 14, 22), 144 (Days 7, 15, 23), and 168 (Days 8, 16, 24) hours after dosing. Acceptable PK sampling windows are provided in [Table 11-1](#). At the Safety Follow-up Visit, a single blood sample for PK analysis will be collected.

h Study drug will be administered as a suspension in the fed state on the Day 1 Visit, as a tablet in the fed state on the Day 9 Visit, and as a tablet in the fed state and with milk on the Day 17 Visit ([Section 9.6.1](#)).

i All medications taken from 28 days before the first dose of study drug through the end of the study will be recorded.

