#### **9.1.1.3 Follow-up**

Subjects will have a Safety Follow-up Visit 7 to 10 days after the last study drug dose. Safety Follow-up Visit assessments are listed in [Table 3-2](#) (Cohorts A1 through A6 [up to A8]), [Table 3-3](#) (Cohort A3), [Table 3-4](#) (Cohort A9), [Table 3-5](#) (Part B), and [Table 3-6](#) (Part C).

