#### **Part A, Cohort A3: Effect of Milk**

In addition to the above instructions for dosing under fed conditions, on Day 9 (open-label VX-121 suspension, fed state and with milk), administration of the VX-121 suspension will be followed by a glass of skim milk (240 mL). Water will be consumed with dosing as needed to rinse suspension from the dosing vial. Refer to the FPI for additional information.

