#### **Part A, Cohort A9: Relative Bioavailability and Effect of Milk**

On the Day 1, 9, and 17 Visits (fed state), subjects must abstain from all food and drink (except water) at least 8 hours before the start of the standard breakfast. A standard breakfast, containing approximately 20 g of fat, will be served to subjects 30 minutes before dosing. Subjects must complete the entire meal in 30 minutes or less; study drug will be administered 30 minutes after the start of the meal. Food will not be permitted for at least 4 hours after dosing. Water (including clear liquids) may be consumed without restriction beginning 1 hour after dosing. On Day 17 (tablet, fed state and with milk), administration of the VX-121 tablet will occur with a glass of skim milk (240 mL) instead of water.

Lunch will be provided approximately 4 to 5 hours after dosing. Dinner will be provided approximately 9 to 10 hours after dosing.

An evening snack will be permitted.

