9.4.1 Adverse Events

AEs will be coded according to MedDRA (Version 20.1 or above). The number and percentage of subjects experiencing an AE will be summarized by the MedDRA System Organ Class (SOC) and Preferred Term (PT). AEs will be classified as pretreatment or treatment-emergent.

Pretreatment AEs are defined as AEs that were reported or worsened (either in severity or seriousness) after signing the ICF up to the start of study drug dosing.

Treatment-emergent adverse events (TEAEs) for all cohorts except Cohorts A3 and A9 are defined as any AE that worsened (either in severity or seriousness) or that was newly developed at or after the first dose date of study drug during the Treatment Period through the end of the TE Period for the Treatment Period.

For Cohort A3 and A9, TEAEs will be assigned to each treatment group based on the start date of the AE and the start of study drug administration dates within the corresponding TE Period.

For AEs with completely missing or partially missing start dates, if there is no clear evidence that the AEs started before or after study treatment, the AEs will be classified as TEAEs corresponding to the Treatment Period. Unless otherwise specified, TEAE refers to TEAE during the Treatment Period.

Details for imputing missing or partial start dates of adverse events are described in [Appendix C](#), which is applicable to Part D only.

AE summary tables will be presented for TEAEs only and will include the following: (1) Overview of TEAEs (2) all TEAE; (3) related (defined as possibly related, related, or missing) TEAEs; (4) serious TEAEs; (5) TEAEs by severity; (6) TEAEs by relationship; and (7) TEAEs leading to treatment discontinuation.

Summaries will be presented using frequency counts and percentages by treatment group/treatment sequence for each part (i.e., number and percentage of subjects with an event); for the summary table of TEAE Overview, an additional column of overall will be provided.

When summarizing the number and percentages of subjects, subjects with multiple occurrences of the same adverse event will be counted once, and only the maximum severity level will be presented in the severity summaries, and the strongest relationship level in the relationship summaries.

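### Cohort A9, and apparently A3, schedule one safety lab about 24 h after each non-final dose and none before the next, so a late-starting laboratory AE could be counted under the following treatment

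*SAP*

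**What the plan says.** **Schedule, Cohort A9.** In Protocol Table 3-4 the row "Serum chemistry" and the hematology row are marked on Days -1, 2, 10 and 18 and at Safety Follow-up. Protocol Section 9.6.1 gives the dosing days: "On the Day 1, 9, and 17 Visits (fed state". Footnote g schedules PK blood predose on the same days: "Blood samples for PK assessments will be collected on Days 1, 9, and 17 before dosing (0 hours".

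**Schedule, Cohort A3.** Table 3-3 appears to mark the same panels on Days -1, 2 and 10 and at follow-up. The first dose is on Day 1 and the second is "on Day 9 (open-label VX-121 suspension, fed state and with milk". Footnote a of the table states: "On dosing days, assessments will be performed before dosing, unless noted otherwise".

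**Late visit.** Protocol Section 9.1.1.3: "Subjects will have a Safety Follow-up Visit 7 to 10 days after the last study drug dose".

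**Analysis.** SAP Section 9.1 ends each non-final treatment-emergent (TE) period in A3 and A9 when the next dose is given. It defines a single baseline, the last value before the first dose. SAP Section 9.4.1 says that in these two cohorts "TEAEs will be assigned to each treatment group based on the start date of the AE" and the dosing dates. SAP Section 9.4.2 says that clinically significant laboratory findings become AEs, and that laboratory "results including baseline and change from baseline values will be summarized at each scheduled time point by treatment group/treatment sequence".

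**The concern.** Laboratory results are a named component of the primary safety endpoint, and the SAP reports A3 and A9 by treatment condition. For that to work, a finding has to be datable to the period in which it arose. After the 24 h sample, the next scheduled chemistry or hematology result comes about 24 h into the following treatment. An abnormality without symptoms that begins in between has no earlier sample to date it.

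Other parts of the protocol avoid this gap. The ordinary single-dose cohorts (Table 3-2) have labs on Day 2 and again 7 to 10 days after their one dose. A9 ECGs are repeated predose on Days 9 and 17 (Table 3-4, footnote e). The 8-day interval in A9 is justified in Protocol Section 9.3.1 as limiting carryover, yet no scheduled safety lab looks for carryover before the next dose.

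At stake are the by-treatment AE counts and, to a lesser degree, the interpretation of the Day 10 and Day 18 changes from baseline.

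**Working it through.** The documents give no numerical figure on this point, so the check is a count of samples against doses and TE-period boundaries.

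**Inputs.** Lab days: Tables 3-3 and 3-4. Dose days: Table 3-3 footnotes e and g, Table 3-4 footnotes g and h, and Section 9.6.1. Follow-up: 7 to 10 days after the last dose, which is Days 9 + 7 = 16 to 9 + 10 = 19 in A3 and Days 17 + 7 = 24 to 17 + 10 = 27 in A9. Hours after a dose = (sample day − dose day) × 24.

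| Treatment | Dose day | Scheduled labs before any further dose | Next scheduled lab |
|---|---|---|---|
| A9 suspension | 1 | Day 2: 24 h | Day 10: (10 − 1) × 24 = 216 h, which is 24 h after the next dose |
| A9 tablet | 9 | Day 10: 24 h | Day 18: (18 − 9) × 24 = 216 h, which is 24 h after the next dose |
| A9 tablet with milk | 17 | Day 18: 24 h; follow-up: 168 to 240 h | none |
| A3 randomized dose | 1 | Day 2: 24 h | Day 10, if confirmed: 216 h, which is 24 h after the next dose |
| A3 suspension with milk | 9 | Day 10, if confirmed: 24 h; follow-up: 168 to 240 h | none |

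**Coverage gap.** Interval between doses = 8 × 24 = 192 h. Time after the only scheduled lab = 192 − 24 = 168 h. Share = 168/192 = 87.5%. This is a share of time. It is not the probability that a finding is misassigned.

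**Attribution.** The non-final TE periods close on Day 9 (A3) and on Days 9 and 17 (A9). A persistent, asymptomatic abnormality first seen on Day 10 or 18 would normally take a start date in the new period and be counted there. A transient one would be missed, not moved.

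**Continuous summaries.** The Day 2, 10 and 18 rows each lie 24 h after a dose, so they are alike in timing. All use the baseline from before Day 1. The Day 10 change is therefore taken 24 h after dose 2 but also 216 h after dose 1, and the Day 18 change 24 h, 216 h and (18 − 1) × 24 = 408 h after doses 3, 2 and 1.

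**Reading of the tables.** In the text copy, Table 3-3 rows are one cell short, and the third lab mark shares a column with the second dosing mark. That column is labelled Day 10, although the footnotes and Section 9.6.1 put the dose on Day 9. By analogy with A9 (Days 2, 10, 18), Day 10 is the consistent reading for the labs, but it is an inference. If the mark belongs to Day 9, footnote a makes the draw predose and the point falls away for A3. In Table 3-4 the first dosing mark sits under Day 2 in the text copy, but footnotes g and h and Section 9.6.1 all say Day 1. The A9 lab rows are not in doubt.

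**The case against.** The strongest reply is that the schedule distorts very little of what is reported.

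- **Laboratory tables.** Labs are summarized by time point, so 24 h values are compared with 24 h values and follow-up stands apart. A reader might infer that the last treatment, with twice as many looks, is made to appear worse. That would be true of an any-time incidence or worst-value table, but none is planned for Part A laboratory data: SAP Table 9-1 confines threshold analysis to Part D. This objection stands.
- **AE route.** Protocol Section 13.1.1.2 requires symptoms, further testing or intervention, or a change in dosing or participation before an abnormal result is clinically significant. Subjects are inpatients, Section 11.7.2 allows unscheduled labs, and Section 13.1.1.3 records first occurrence, so a symptomatic event keeps its true date. This narrows the point to asymptomatic, persistent findings that are still reported as AEs. It does not close it, because these are the findings that nothing earlier can date.
- **Detection rates.** A reader might turn the gap into rates of 12.5% in the correct period for earlier treatments and about 100% for the last. That assumes onset is uniform over 8 days and always persists. The documents give no onset distribution, and the share arising after 24 h could be anything from none to all. Nor is the last treatment fully covered: a day-7 visit cannot see day-8 onset, and A3 TE Period 2 closes at the earlier of follow-up and 7 days after the last dose, so a new finding at a later visit falls outside it.
- **Placebo in A3.** A reader might infer a general shift of findings from placebo to VX-121. With 8 subjects randomized 3:1, about 2 are on placebo, and the SAP labels A3 by sequence, which keeps them visible.
- **Purpose.** The milk and formulation objectives are PK objectives, and safety is descriptive. Cohort A1, planned at 10 mg, has its own 7- to 10-day labs after a single dose. This limits the importance of the point but does not supply the missing attribution rule.

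**Conclusion.** The point holds for Cohort A9, and conditionally for A3. In A9 the first two treatments each have one scheduled chemistry and hematology sample, at about 24 h, and none in the remaining 168 of 192 h. Only the third also has a sample at 7 to 10 days. Under the SAP's period boundaries and start-date rule, an asymptomatic abnormality that arises after the 24 h sample, persists to the next one and is reported as an AE would be counted under the following treatment. Day 10 and Day 18 changes from the single baseline can contain effects of an earlier dose.

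The size is modest: about 8 subjects per cohort, single planned doses of 5 mg (A3) and 10 mg (A9), and descriptive reporting. The documents do not support a stronger claim that the laboratory comparison between conditions is biased throughout, or any numerical misattribution rate. The conclusion rests on doses being given on the scheduled days, on no unscheduled lab falling in the gap and, for A3, on the lab day being Day 10.

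**What to change.** 1. Confirm from the formatted Table 3-3 whether the A3 lab mark is on Day 9 or Day 10.
2. In Table 3-4, add chemistry and hematology to the predose blood draw already scheduled on Days 9 and 17. If the A3 mark is Day 10, do the same on Day 9 in Table 3-3. Each non-final treatment then has a second look at (9 − 1) × 24 = (17 − 9) × 24 = 192 h, before its TE period ends.
3. State in the SAP that this predose sample belongs to the period that is ending.
4. Keep the value before the first dose as the main baseline. Show change from the period's own predose value only as a supplementary summary, because re-baselining at each period would absorb carryover and hide it.
5. If sampling can no longer be changed, have the SAP flag abnormalities first seen on Day 10 or Day 18 as not attributable to a single period.

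**Cost.** A9: 8 × 2 = 16 panels. A3, if needed: 8 × 1 = 8. At most 16 + 8 = 24 routine local-laboratory panels, taken at an existing draw in inpatients, with a small added blood volume and a few lines of SAP text.

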### **8.2.2 Exclusion Criteria**

1. History of any comorbidity that, in the opinion of the investigator, might confound the results of the study or pose an additional risk in administering study drug to the subject.
2. History of clinically significant cirrhosis with or without portal hypertension.
3. Risk factors for Torsade de Pointes and other ventricular arrhythmias, including but not limited to, history of any of the following: familial long QT syndrome, chronic hypokalemia, heart failure, left ventricular hypertrophy, chronic bradycardia, myocardial infarction, cardiomyopathy, history of arrhythmia (ventricular or atrial fibrillation), obesity, acute neurologic events (subarachnoid hemorrhage, intracranial hemorrhage, cerebrovascular accident, or intracranial trauma), or autonomic neuropathy.
4. Any of the following abnormal laboratory values at screening:
  - Hemoglobin  $< 10$  g/dL
  - Total bilirubin  $\geq 2 \times$  ULN
  - Aspartate transaminase (AST), alanine transaminase (ALT), gamma-glutamyl transferase (GGT), or alkaline phosphatase (ALP)  $\geq 3 \times$  ULN
  - Abnormal renal function defined as glomerular filtration rate  $\leq 50$  mL/min/1.73 m^2 (calculated by the Modification of Diet in Renal Disease Study Equation) for subjects  $\geq 18$  years of age

5. An acute upper or lower respiratory infection, pulmonary exacerbation, or changes in therapy (including antibiotics) for sinopulmonary disease within 28 days before the first dose of study drug.
6. Lung infection with organisms associated with a more rapid decline in pulmonary status (e.g., *Burkholderia cenocepacia*, *Burkholderia dolosa*, and *Mycobacterium abscessus*). For subjects who have had a history of a positive culture, the investigator will apply the following criteria to establish whether the subject is free of infection with such organisms:
  - The subject has not had a respiratory tract culture positive for these organisms within the 12 months before the date of informed consent.
  - The subject has had at least 2 respiratory tract cultures negative for such organisms within the 12 months before the date of informed consent, with the first and last of these separated by at least 3 months, and the most recent 1 within the 6 months before the date of informed consent.
7. An acute illness not related to CF (e.g., gastroenteritis) within 14 days before the first dose of study drug.

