## 9.1.2 Part D (Subjects With CF)

A schematic of the study design for Part D is shown in [Figure 9-1](#), which has a randomized, double-blind, placebo-controlled, parallel-group design. After completing the Screening Period, approximately 12 subjects will be randomized 3:1 to TC:placebo.

Screening in Part D will be initiated after the completion of Parts A, B, and C (cohorts needed for Part D dose selection only) through the Safety Follow-up Visit. The decision to proceed to Part D will be based on an evaluation of safety, tolerability, and PK data from completed cohorts in Parts A, B, and C. These data will be submitted to the IEC for approval before proceeding to screening for Part D. Refer to [Section 9.3.2](#) for additional details.

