**Figure 9-1 Schematic of Study Design for Part D**

Screening Period 4 weeks	Treatment Period a 4 weeks	Safety Follow-up Period 4 weeks
	N = 9 VX-121 + TEZ/IVA	
	N = 3 Placebo	

a The planned VX-121 dose for Part D is 10 mg qd. This dose is predicted to provide an approximate AUC0-24h of 10 µg·h/mL, which is within the predicted efficacious exposure range based on in vitro data. Based on emerging safety, tolerability, and PK data from Parts A, B, and C, the planned dose for Part D may be lowered to 5 mg qd. The total daily dose of VX-121 in Part D will be at least 1 dose level below the highest total daily dose tested in Part C. The dosage of TEZ/IVA in the TC will be TEZ 100 mg qd/IVA 150 mg q12h, which will be administered as TEZ 100 mg/IVA 150 mg FDC in the morning and IVA 150 mg in the evening.

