## **9.8.2 Part D**

The medical monitor should be notified of a discontinuation of study drug or an interruption of study drug that lasts >72 hours for any reason and of the resumption of study drug after such interruption.

Subjects with new treatment-emergent ALT or AST elevations of  $>3 \times \text{ULN}$ , or total bilirubin  $>2 \times \text{ULN}$ , must be followed closely, including confirmatory testing performed by the central laboratory within 48 to 72 hours of the initial finding and subsequent close monitoring of ALT, AST, and bilirubin levels, as clinically indicated.

If a subject cannot return to the site for confirmatory testing, a local laboratory may be used. Local laboratory results must be reported immediately to the medical monitor, and the subject must have the tests repeated and sent to the central laboratory as soon as possible (ideally within 48 to 72 hours).

Study drug administration **must be interrupted** immediately (prior to confirmatory testing) if any of the following criteria are met:

- ALT or AST  $>8 \times$  ULN
- ALT or AST  $>5 \times$  ULN for more than 2 weeks
- ALT or AST  $>3 \times$  ULN, in association with total bilirubin  $>2 \times$  ULN and/or clinical jaundice

A thorough investigation of potential causes should be conducted, and the subject should be followed closely for clinical progression.

Study drug administration **must be discontinued** if subsequent ALT or AST values confirm the initial elevation that satisfied the interruption rule (above), and no convincing alternative etiology (e.g., acetaminophen use, viral hepatitis, alcohol ingestion) is identified, regardless of whether transaminase levels have improved.

All subjects in whom treatment is discontinued for elevated transaminases and/or bilirubin should have these levels monitored closely until levels normalize or return to baseline.

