Appendix D: Criteria for Threshold Analysis

Table 12-2 Threshold Analysis Criteria for Laboratory Tests (as applicable)

Parameter	Threshold Analysis	Comments
Clinical Chemistry (LFT)		
ALT	
 >ULN - $\leq 3 \times$ULN $>3x - \leq 5x$ULN $>5x - \leq 8x$ULN $>8x - \leq 20.0x$ULN $>20.0x$ULN 	FDA DILI Guidance Jul 2009.
AST	
 >ULN - $\leq 3 \times$ULN $>3x - \leq 5x$ULN $>5x - \leq 8x$ULN $>8x - \leq 20.0x$ULN $>20.0x$ULN 	FDA DILI Guidance Jul 2009.
ALT or AST	
 (ALT>ULN - $\leq 3 \times$ULN) or (AST>ULN - $\leq 3 \times$ULN) (ALT>3x - $\leq 5x$ULN) or (AST>3x - $\leq 5x$ULN) (ALT>5x - $\leq 8x$ULN) or (AST>5x - $\leq 8x$ULN) (ALT>8x - $\leq 20x$ULN) or (AST>8x - $\leq 20x$ULN) ALT>20xULN or AST> 20 xULN 	FDA DILI Guidance
Alkaline Phosphatase	
 >ULN - $\leq 1.5 \times$ULN $>1.5 - \leq 2.5 \times$ULN $>2.5 - \leq 5.0 \times$ULN $>5.0 - \leq 20.0 \times$ULN $>20.0 \times$ULN 	FDA DILI Guidance Jul 2009.
Total Bilirubin	
 >ULN - $\leq 1.5 \times$ULN $>1.5 - \leq 2 \times$ULN $>2 - \leq 3 \times$ULN $>3 - \leq 10 \times$ULN $>10 \times$ULN 	FDA DILI Guidance Jul 2009.
Direct Bilirubin	
 >ULN - $\leq 1.5 \times$ULN $>1.5 - \leq 2 \times$ULN $>2 - \leq 3 \times$ULN $>3 - \leq 10 \times$ULN $>10 \times$ULN 	FDA DILI Guidance Jul 2009.
ALT and Total Bilirubin	ALT>3xULN and TBILI>2xULN	FDA DILI Guidance Jul 2009.
AST and Total Bilirubin	AST>3xULN and TBILI>2xULN	FDA DILI Guidance Jul 2009.
(ALT or AST) and Total Bilirubin (ALT>3xULN or AST>3xULN) and FDA DILI Guidance Jul 2009. TBILI>2xULN		

Table 12-2 Threshold Analysis Criteria for Laboratory Tests (as applicable)

Parameter	Threshold Analysis	Comments
GGT	>ULN - $\leq 2.5 \times \text{ULN}$ $>2.5 - \leq 5.0 \times \text{ULN}$ $>5.0 - \leq 20.0 \times \text{ULN}$ $>20.0 \times \text{ULN}$	CTCAE grade 1-4
Clinical Chemistry (NON-LFT)		
Albumin	<LLN - $\geq 30 \text{ g/L}$ $<30 - \geq 20 \text{ g/L}$ $<20 \text{ g/L}$	CTCAE grade 1-3
Amylase	>1x - $\leq 1.5 \times \text{ULN}$ $>1.5x - \leq 2 \times \text{ULN}$ $>2x - \leq 5 \times \text{ULN}$ $>5 \times \text{ULN}$	Criteria based upon CTCAE
Creatinine	>ULN - $\leq 1.5 \times \text{ULN}$ $>1.5 - \leq 3.0 \times \text{ULN}$ $>3.0 - \leq 6.0 \times \text{ULN}$ $>6.0 \times \text{ULN}$	CTCAE grades 1-4

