Note: Based on CPMP 1997 guideline.

Table 12-4 Threshold Analysis Criteria for Vital Signs

Parameter	Threshold Analysis	Comments
Pulse Rate	Same as above in ECG category	
SBP increased	>140 mmHg >160 mmHg >10 mmHg increase from baseline >20 mmHg increase from baseline >140 mmHg & >10 mmHg increase from baseline >140 mmHg & >20 mmHg increase from baseline >160 mmHg & >10 mmHg increase from baseline >160 mmHg & >20 mmHg increase from baseline	809/770 analyses

Table 12-4 Threshold Analysis Criteria for Vital Signs

Parameter	Threshold Analysis	Comments
SBP decrease	<90 mmHg <80 mmHg >10 mmHg decrease from baseline >20 mmHg decrease from baseline <90 mmHg and >10 mmHg decrease from baseline <90 mmHg and >20 mmHg decrease from baseline <80 mmHg and >10 mmHg decrease from baseline <80 mmHg and >20 mmHg decrease from baseline	Per HV grade 1, 3, plus shift change
DBP increased	>90 mmHg >100 mmHg >5 mmHg increase from baseline >10 mmHg increase from baseline >90 mmHg and >5 mmHg increase from baseline >90 mmHg and >10 mmHg increase from baseline >100 mmHg and >5 mmHg increase from baseline >100 mmHg and >10 mmHg increase from baseline	
DBP decreased	<60 mmHg <45 mmHg >5 mmHg decrease from baseline >10 mmHg decrease from baseline <60 mmHg and >5 mmHg decrease from baseline <60 mmHg and >10 mmHg decrease from baseline <45 mmHg and >5 mmHg decrease from baseline <45 mmHg and >10 mmHg decrease from baseline	

Table 12-4 Threshold Analysis Criteria for Vital Signs

Parameter	Threshold Analysis	Comments
Weight	Weight gain ≥5 % increase from baseline ≥10 % increase from baseline ≥ 20% increase from baseline	CTCAE grade 1-3
	Weight loss ≥5 % decrease from baseline ≥10 % decrease from baseline ≥ 20% decrease from baseline	CTCAE grade 1-3

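### Part D laboratory threshold counts ignore baseline and no shift table is planned, so unchanged mild abnormalities admitted at entry appear as on-treatment cases

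*SAP*

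**What the plan says.** SAP 9.4.2 plans, for Part D and by treatment group, a summary of "the number and percentage of subjects meeting at least 1 threshold analysis criterion event, during the TE period for Treatment Period", with criteria in Appendix D. The treatment-emergent (TE) period runs from the first dose date to the Safety Follow-up Visit, or to 28 days after the last dose if there is no such visit (SAP 9.1).

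Every laboratory row in Table 12-2 is a multiple of ULN, a position relative to LLN or ULN, or an absolute value. No row or note mentions baseline. SAP Table 9-1 lists raw values, change from baseline, a listing of clinical abnormalities and the threshold analysis for hematology and chemistry. It has no shift table.

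Protocol 8.2.2, item 4, excludes subjects with "Any of the following abnormal laboratory values at screening": hemoglobin <10 g/dL, total bilirubin >=2xULN, AST, ALT, GGT or ALP >=3xULN, and GFR <=50 mL/min/1.73 m². The other Table 12-2 tests have no numeric limit of their own; creatinine is limited only indirectly, through GFR.

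In Part D, "approximately 12 subjects will be randomized 3:1 to TC:placebo" (Protocol 9.1.2). Figure 9-1 shows "N = 9 VX-121 + TEZ/IVA" and 3 on placebo.

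**The concern.** Laboratory results are part of the primary safety endpoint (Protocol 7.1, SAP 6.1). The threshold table is the only planned categorical laboratory summary, and it cannot tell a subject who became abnormal on treatment from one who arrived abnormal and stayed so. In arms of 9 and 3, one or two such subjects can shape the comparison a reader takes away.

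Other parts of the plan do refer to baseline:

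- Tables 12-3 and 12-4 include criteria on change from baseline, some combined with a level, such as "<90 mmHg and >10 mmHg decrease from baseline".
- TEAEs must be new or worsened (SAP 9.4.1).
- Protocol 9.8.2 begins its liver monitoring rule with "Subjects with new treatment-emergent ALT or AST elevations of" a stated size.

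Table 12-2 is the only one of the three Appendix D threshold tables with no baseline-referenced criterion.

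**Working it through.** **Arm sizes.** 12 x 3/4 = 9 and 12 x 1/4 = 3, which matches Protocol Figure 9-1. One subject is 1/9 = 11.1% of the triple-combination arm or 1/3 = 33.3% of placebo.

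**Which categories can an admitted screening value already occupy?** Entry limits (Protocol 8.2.2) against Table 12-2:

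| Test | Admitted at screening | Categories it can occupy | Out of reach if unchanged |
|---|---|---|---|
| ALT, AST | <3xULN | >1–3x | >3x and above |
| ALP | <3xULN | >1–1.5x, >1.5–2.5x, >2.5–5x (values below 3x) | >5x and above |
| GGT | <3xULN | >1–2.5x, >2.5–5x (values below 3x) | >5x and above |
| Total bilirubin | <2xULN | >1–1.5x, >1.5–2x | >2x and above |
| ALT or AST with total bilirubin | as above | none | all combined rows |
| Hemoglobin, low | >=100 g/L | <LLN to 100 g/L | <100 g/L |
| CK, amylase, lipase, albumin, total protein, platelets, reticulocytes, direct bilirubin, coagulation | no numeric limit | any | none by rule |

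The limits apply at screening, while SAP 9.1 takes the last pre-dose value as baseline. A Day 1 value could therefore have drifted past a limit, and the last column holds only for values unchanged since screening.

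**How often would unchanged abnormalities alone produce a contrast?** The documents give no baseline prevalence. Assume that a share p of subjects starts in a counted category of a given test, that each such abnormality is still present in a post-dose sample, and that no one else crosses a threshold.

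- Expected counts: 9p on triple combination, 3p on placebo.
- P(at least 1 on triple combination, 0 on placebo) = (1-p)^3 x [1-(1-p)^9].
- P(0 on triple combination, at least 1 on placebo) = (1-p)^9 x [1-(1-p)^3].

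| p | 9p | 3p | Triple combination only | Placebo only |
|---|---|---|---|---|
| 10% | 0.9 | 0.3 | 0.729 x 0.613 = 0.447 | 0.387 x 0.271 = 0.105 |
| 20% | 1.8 | 0.6 | 0.512 x 0.866 = 0.443 | 0.134 x 0.488 = 0.065 |
| 30% | 2.7 | 0.9 | 0.343 x 0.960 = 0.329 | 0.040 x 0.657 = 0.027 |

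The chance that the two arm percentages differ by 20 points or more in either direction is 0.38, 0.57 and 0.60.

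**A case without a prevalence assumption.** Suppose exactly 2 of the 12 enter with a stable abnormality. There are C(12,2) = 66 ways to place them:

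- both on triple combination: 36/66 = 0.545, shown as 22.2% vs 0%
- one in each arm: 27/66 = 0.409, shown as 11.1% vs 33.3%
- both on placebo: 3/66 = 0.045, shown as 0% vs 66.7%

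The expected percentage is the same in both arms: 0.545 x 22.2 + 0.409 x 11.1 = 16.7, and 0.409 x 33.3 + 0.045 x 66.7 = 16.7. Baseline abnormality therefore adds noise, with no systematic tilt toward either arm.

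**The case against.** The strongest reply is that the information is already there. SAP 9.4.2 summarizes baseline and change from baseline at each time point, all subject data are listed, and a laboratory finding becomes an AE only on clinically significant worsening from baseline (Protocol 13.1.1.2). With about 12 subjects, a reader can trace any count by hand. No hypothesis test uses the safety data, and no stopping or dosing rule cites this table. This stands, and it limits the weight of the point. It does not remove it: arm-level means do not show whether a counted subject was already abnormal, and listings leave the reader to build the missing table.

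It is also fair that Tables 12-3 and 12-4 contain stand-alone absolute rows, so absolute counts are normal in this appendix. The Protocol 9.8.2 wording is a monitoring trigger and not an analysis definition. For tests with no numeric limit, Protocol 8.2.2, item 1, still lets the investigator exclude a subject whose comorbidity could confound results or add risk.

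A reader might infer three stronger things that the documents do not support:

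- **That the main liver-injury rows are inflated.** An unchanged admitted screening value cannot reach them.
- **That the table is biased against the drug.** Randomization gives equal expected percentages. The triple-combination-only pattern is the commoner one-sided result because that arm is three times larger, and newly arising background abnormalities would show it too.
- **That the absolute counts should give way to a rule counting only a worse category than baseline.** That rule would drop a subject whose ALT rises from 1.1x to 2.9xULN, because both values lie in one category.

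**Conclusion.** The point holds in a limited form. As written, the Part D laboratory threshold table mixes pre-existing with emergent abnormality in the lower ALT/AST category, ALP and GGT below 3xULN, total bilirubin below 2xULN, mild anemia, and tests without a numeric entry limit. Each unchanged subject moves a row by 11.1 points on triple combination or 33.3 on placebo.

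The category overlap and these step sizes follow directly from the documents. The probabilities of 0.447, 0.443 and 0.329 rest on assumed prevalences of 10%, 20% and 30% and on every abnormality persisting after dosing. The consequence is harder interpretation of a descriptive table; no test or error rate is affected. It is worth fixing because it is cheap.

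**What to change.** In SAP 9.4.2 and Table 9-1, keep the absolute threshold counts and add, for Part D, a shift table of baseline category by worst TE-period category for each Table 12-2 parameter:

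- Use the Table 12-2 categories plus a category for values that meet no criterion.
- For two-sided tests (hemoglobin, platelets, total protein, reticulocytes), tabulate the low and high directions separately.
- Use as denominator the subjects with a baseline and at least 1 post-dose value.
- Take the worst category from post-dose values only, because the TE period starts on the first dose date and the Day 1 pre-dose sample may fall on it.

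A shift table will not show a rise within one category; the planned change-from-baseline summaries and listings must still cover that. The cost is SAP wording and one extra set of tables, with no new data. SAP section 4 allows such an amendment before database lock.
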